3.8.5 Subgroups to be Analyzed

Descriptive statistics will be presented separately by age group (randomization stratification variable: age 4 to 8 years versus age 9 to 12 years) for the primary and the two key secondary endpoints. Observed values will be reported by treatment group. The difference in means or proportions for OV101 versus placebo will also be presented with the corresponding 95% confidence intervals. Similar subgroup analysis will be conducted for region (US versus outside US).

If for a given endpoint, the results in the two subgroups appear different from a clinical perspective, the appropriate model (MMRM, generalized logit, or logistic) could be constructed as described above, including an age-by-treatment interaction term. This interaction term will be tested at alpha level of 0.100 to assess whether the treatment effects are statistically significantly different for the two age subgroups.

3.8.6 Missing Data Handling and Sensitivity Analysis

All analyses involving imputation of missing efficacy data will be accompanied with a descriptive table showing the number and percentage of missing endpoint values by visit and treatment group. The reasons of missing, if captured, will be also displayed.

Primary Analysis – CGI-I-AS

The primary endpoint, CGI-I-AS scale assessed by the clinician will be collected at the Week 6 and 12 visits. This is an ordinal variable with scores ranging from 1 (very much improved), 4 (no change), to 7 (very much worse) which will be analyzed as a continuous outcome variable in the analyses.

For the primary analysis of CGI-I-AS, missing data will not be imputed. The primary analysis will be based on all available data at the mapped visits (Table 2) at Week 6

and Week 12 as captured in the clinical database, using a MMRM ANOVA model with fixed effects for visit (Weeks 6 and 12), randomized treatment, the visit-by-treatment interaction, and age group (randomization stratification variable: age 4 to 8 years versus age 9 to 12 years) and region (randomization stratification variable: US versus outside US). MMRM models implicitly adjust for missing data under a missing at random (MAR) assumption.

Sensitivity Analyses Using Multiple Imputation – CGI-I-AS

If more than 3% of CGI-I-AS values at Week 12 are missing, as a sensitivity analysis, missing data will be imputed using the multiple imputation (MI) procedure. The imputation strategy described in Ouyang (2017) will be implemented for this study. There are only two visits where CGI-I-AS is assessed, hence, there are 2 possible missing patterns in the CGI-I-AS data: 1) Week 6 assessment is missing and Week 12 assessment is present (non-monotone pattern); or 2) Week 12 assessment is missing but Week 6 assessment is present (monotone pattern). In general, the MAR assumption is reasonable for intermittent missing values before a subject is discontinued because the data before and after the intermittent missing value are known. In this case, if Week 6 CGI-I-AS is missing but Week 12 CGI-I-AS is assessed (missing data pattern 1), it is reasonable to consider the missing Week 6 data as MAR. However, missing CGI-I-AS at Week 12 after the subject is withdrawn from the trial may or may not be MAR. Multiple imputation will first be implemented under the MAR assumption. To assess the appropriateness of the MAR assumption, additional sensitivity analyses using a tipping point approach will be performed under scenarios assuming missing not at random (MNAR) for the missing data pattern 2 above.

Multiple Imputation Procedure under MAR assumption will be conducted as follows using SAS PROC MI:

1. Missing Week 6 CGI-I-AS data points will be imputed under MAR assumption using a logistic regression model for ordinal data with randomized treatment, age group, region, and CGI-S-AS Overall Score at Baseline as independent variables.
2. Missing Week 12 CGI-I-AS data points will be imputed under MAR assumption using a logistic regression model for ordinal data with randomized treatment, age group, region, CGI-S-AS Overall Score at Baseline, and the Week 6 CGI-I-AS as independent variables.
3. Thirty complete imputed datasets will be generated by repeating the above steps 30 times.
4. The primary MMRM analysis of CGI-I-AS described above will be performed for each of the 30 complete imputed data sets.

5. The estimated treatment effects will be combined across the 30 analyses using SAS PROC MIANALYZE.

If the treatment effect is significant in the analysis using the MI procedure under MAR, with significance level of 0.05 and more than 5% of CGI-I-AS values at Week 12 are missing, a tipping point analysis will be conducted.

The tipping point analysis will focus on the imputed CGI-I-AS values which may be MNAR (missing data pattern 2 above). These analyses will start with the 30 imputed datasets created under a MAR assumption as described above. For each dataset, the imputed values of CGI-I-AS for the OV101 group (with missing pattern 2) will be worsened by adding 1 (unless the current value is the highest level on the CGI-I-AS scale [7=very much worse]). The placebo group imputed values will remain unchanged. After the OV101 group's imputed Week 12 CGI-I-AS data have been "worsened" by 1 point for those with missing pattern 2, the MMRM model used in the primary analysis will be fitted to the data and the estimated treatment effects will be combined using SAS PROC MIANALYZE. This process will be repeated, at each step incrementally worsening by 1 the imputed values of CGI-I-AS for the OV101 group, until the treatment effect is no longer significant (p-value for the treatment comparison ≥ 0.05).

As a sensitivity analysis, the following rank-based imputation strategy described in Ouyang (2017) will also be implemented when more than 5% of CGI-I-AS values at Week 12 are missing. This analysis will include both subjects with a Week 12 CGI-I-AS and subjects who discontinued prior to the Week 12 assessment, without the need for multiple imputation methodology and the associated assumptions. This approach assumes that discontinuation from the trial is detrimental so it penalizes the treatment group with more early discontinuations. The subjects will be first divided into 2 sets according to their CGI-I-AS assessments: 1) those with a Week 12 CGI-I-AS; and 2) those with a Week 6 CGI-I-AS but no Week 12 CGI-I-AS. Within the two sets, subjects will be ranked separately (based on the Week 12 CGI-I-AS for set 1 and the Week 6 CGI-I-AS for set 2). The lowest rank will be given to the largest CGI-I-AS within that set. The Wilcoxon Rank-Sum test will then be applied to this ranking instead of ranking solely based on the Week 12 CGI-I-AS for completers.

As described in Section 3.8.3, MMRM Analysis of Covariance (ANCOVA) models for the change from Baseline will be fitted for each [REDACTED] endpoint with fixed effects for visit (Weeks 6 and 12), randomized treatment, the visit-by-treatment interaction, age group, region, and the corresponding Baseline as a covariate. Missing data will not be imputed in the main analyses, but MMRM models implicitly adjust for missing data under a missing at random (MAR) assumption.

[REDACTED]

Based on visit average values, if more than 5% but not more than 20% of [REDACTED] data are missing at Week 12, as sensitivity analyses for each [REDACTED] secondary endpoint, missing data will be imputed using a multiple imputation procedure under a MAR assumption as follows:

1. Missing Week 6 [REDACTED] data points will be imputed under a MAR assumption using a linear regression model with randomized treatment, age group, region, and the corresponding baseline as independent variables.
2. Missing Week 12 [REDACTED] data points will be imputed under MAR assumption using a linear regression model with randomized treatment, age group, region, and the corresponding baseline and Week 6 [REDACTED] variable as independent variables.
3. Thirty complete imputed datasets will be generated by repeating the above steps 30 times.
4. The primary MMRM analysis of each [REDACTED] endpoint as described above will be performed for each of the 30 complete imputed data sets.
5. The estimated treatment effects will be combined across the 30 analyses using SAS PROC MIANALYZE.

If there is more than 20% of data missing for [REDACTED] endpoints, then baseline characteristics (including Baseline CGI-S-AS) will be compared for the subjects missing the specific [REDACTED] endpoint versus the subjects who are not missing the specific [REDACTED] endpoint, for both treatment groups combined. In this analysis, Baseline CGI-S-AS will be summarized as a continuous variable, with the focus on the mean if the normality assumptions are met for Baseline CGI-S-AS, and the focus on the median if Baseline CGI-S-AS is non-normal. Also, if the prevalence of missing is similar across treatment groups, CGI-I-AS at Week 12 will also be summarized by missing status and treatment group. These analyses will inform the interpretation of the descriptive analysis of the [REDACTED] endpoints.

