3.1.8 Analysis Visit Windows

Visit windows for study conduct are specified in Table 1: Schedule of Activities. Unless otherwise specified, the following analysis visit rules will be implemented for all endpoints [REDACTED] and seizure diary (see sections 3.8.3, 3.8.4, and 3.9.6 for analysis visit window computations). For all unscheduled visits and end of treatment (EOT) visits from subjects discontinuing treatment early (before Week 12), assessments will be mapped according to the analysis visit windows in Table 2 for primary summarization and analysis. If the visit does not fall within any of the analysis visit windows, then the visit will be considered missing at the specified time point for analysis purposes.

Table 2: Nominal (Targeted) Time Points and Analysis Visit Windows

Assessment	Nominal (Targeted) Time Point	Analysis Visit Window (Interval in Study Days)
Baseline Assessments	Study Day 1	≤ Day 1
Phone/Titration (Day 6)	Study Day 6	>Day 1 - ≤Day 8
Phone/Titration (Day 11)	Study Day 11	≥Day 9 - ≤Day 21
Week 6 (Study Day 43)	Study Day 43	≥Day 22 - ≤Day 64
Week 12 (Study Day 85)	Study Day 85	≥Day 65 - ≤Day 92
Week 14 (Study Day 99)	Study Day 99	≥Day 93

After mapping the data from unscheduled and end of treatment (EOT) visits from subjects discontinuing treatment early to the nominal time point, the following rules will apply if multiple records are available within a single analysis visit window unless otherwise specified for a particular analysis:

- If a record exists for the nominal time point, that record will be selected for analysis.
- If a record for the nominal time point does not exist and multiple records are available within a single analysis visit window,
 - The record closest to the planned assessment day will be selected for analysis
 - If 2 records are equidistant from the target day, then the earliest record will be selected (does not apply to the Week 12 or 14 visits).
- If a subject has no record in an analysis window, the subject will be considered missing at that time point.

For the primary and key secondary objectives, a supportive analysis will be conducted in which CGI-I-AS assessments from unscheduled visits and end of treatment (EOT) visits from subjects discontinuing treatment early (before Week 12) will be mapped according to the analysis visit windows in Table 3.

Table 3: Nominal (Targeted) Time Points and Alternative Analysis Visit Windows

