Assessment	Nominal (Targeted) Time Point	Analysis Visit Window (Interval in Study Days)
Baseline Assessments	Study Day 1	≤ Day 1
Week 6 (Study Day 43)	Study Day 43	>Day 1 - ≤Day 43
Week 12 (Study Day 85)	Study Day 85	>Day 43

After mapping the data to the nominal time point, the following rules will apply if multiple records are available within a single analysis visit window unless otherwise specified for a particular analysis:

- If a record exists for the nominal time point, that record will be selected for analysis.
- If a record for the nominal time point does not exist and multiple records are available within a single analysis visit window,
 - The record closest to the planned assessment day will be selected for analysis
 - If 2 records are equidistant from the target day, then the earliest record will be selected (does not apply to the Week 12 visit).
- If a subject has no record in an analysis window, the subject will be considered missing at that time point.

In addition, for the primary and key secondary objectives, an additional supportive analysis will be conducted in which CGI-I-AS assessments will be analyzed according to the nominal visit time point (i.e. only records identified as baseline and records from the Day 43/Week 6 and Day 85/EOT/Week 12 visits will be included).

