3.2 Analysis Populations and Subgroups

3.2.1 Definition of Analysis Populations

The following analysis sets, with the exception of the Intent-to-treat and Safety Set, will only include subjects 4 to 12 years old (inclusive) at screening. The baseline and safety analyses for subjects 2 to 3 years old (inclusive) at screening will be conducted separately.

Intent-to-Treat Analysis Set

The intent-to-treat set (ITT) will consist of all subjects who are randomized (subjects aged 4 to 12 years old (inclusive) or enrolled (subjects aged 2 to 3 years old (inclusive) and meet all inclusion and exclusion criteria), whether or not study drug is received. Subjects aged 4 to 12 years old (inclusive) will be analyzed according to their randomized treatment.

Full Analysis Set

The full analysis set (FAS) will include all subjects aged 4 to 12 years old (inclusive) who are randomized, receive at least 1 dose of study drug, and have at least 1 post-baseline assessment of the primary efficacy endpoint. The FAS will be used for efficacy analyses based on the randomized treatment for each subject.

Per Protocol Set

The per protocol set (PPS) is a subset of the FAS that includes subjects who complete the Week 12 CGI-I-AS assessment (with appropriate visit mapping as shown in Table 2) and have no major protocol deviations that are deemed to impact efficacy. These violations include but are not limited to violations of inclusion/exclusion criteria deemed to impact efficacy, inadequate study drug compliance over the dosing period as determined from the dosing information in the eCRF, usage of prohibited concomitant medications, and incorrect randomization. Additionally, other relevant protocol deviations, such as early termination or interruption of treatment, may be identified for review.

Prior to database lock and unblinding, there will be a meeting to review all protocol deviations to determine PPS exclusions. The threshold for percent compliance that would be considered inadequate and would result in exclusion from the PPS will also be determined in this meeting following review of the relevant compliance

information. The PPS will be used for efficacy analyses based on the randomized treatment for each subject.

Safety Set

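### SAP 3.8.6 omits the both-visits-missing pattern, so the tipping-point and rank analyses apply no penalty to children who withdraw in about the first week

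*SAP*

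**What the plan says.** SAP 3.8.6 states that CGI-I-AS is assessed at two visits and "hence, there are 2 possible missing patterns in the CGI-I-AS data". Pattern 1 is Week 6 missing with Week 12 present; pattern 2 is Week 12 missing with Week 6 present. Multiple imputation under MAR comes first, if more than 3% of Week 12 values are missing. Two further analyses are planned above 5%:

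- **Tipping point** (also requires a significant MAR result). Imputed values in OV101 children "with missing pattern 2) will be worsened by adding 1", repeatedly, until significance is lost.
- **Rank analysis.** One set has a Week 12 score; the other is "those with a Week 6 CGI-I-AS but no Week 12 CGI-I-AS". The SAP says this analysis covers children who stopped before Week 12 and penalises the arm with more early discontinuation.

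SAP 3.1.8 (Table 2) maps early end-of-treatment (EOT) visits by study day: Day 9 to 21 belongs to the Day 11 phone contact, Day 22 to 64 to Week 6, and Day 65 to 92 to Week 12. It adds: "If a subject has no record in an analysis window, the subject will be considered missing at that time point". The same section plans a supportive analysis of "CGI-I-AS assessments from unscheduled visits and end of treatment (EOT) visits from subjects discontinuing treatment early", so such scores are expected to exist.

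SAP 3.2.1 admits to the FAS dosed, randomised children who "have at least 1 post-baseline assessment of the primary efficacy endpoint". The per-protocol set, by contrast, requires that they "complete the Week 12 CGI-I-AS assessment (with appropriate visit mapping as shown in Table 2".

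**The concern.** The list of patterns leaves out the child with neither score. The SAP accepts MAR for pattern 1 because a later score is known, and doubts it for Week 12 data lost after withdrawal. A child with neither score gives more reason for doubt than pattern 2 does, yet receives at most a MAR imputation and is never worsened or ranked low.

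The tipping point and the rank test are the only CGI-I-AS analyses that assume a worse-than-MAR outcome for dropouts. If very early withdrawals sit outside both, the result can look robust by construction, and most so if early withdrawal is commoner on OV101. Protocol 7.13 promises imputation under a missing-not-at-random assumption; these children would not receive it.

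**Working it through.** **1. Number of patterns.** Two visits, each present or missing, give 2 × 2 = 4 combinations, of which 3 have something missing. The SAP's figure of 2 is reproduced only if every child in the analysis must have at least one mapped score.

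**2. Can both be missing under the plan's rules?** Protocol 4.2 asks for the EOT visit within 2 weeks of the last dose when a child is withdrawn early. Protocol 5.2.1 contains a Day 6 tolerability rule that stops study drug, so first-week stops are foreseen.

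| Last dose | Latest EOT | Table 2 window |
|---|---|---|
| Day 5 | 5 + 14 = Day 19 | Day 6 or Day 11 contact |
| Day 7 | 7 + 14 = Day 21 | Day 6 or Day 11 contact |
| Day 8 to 21 | Day 22 to 35 | phone contact or Week 6, depending on the EOT date |
| Day 22 | Day 36 | Week 6 |

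With a last dose by Day 7, an on-time EOT and no later visit, Week 6 and Week 12 are both missing. A Day 11 stop is also affected if the EOT is held within 10 days.

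**3. What happens to that child?**

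| Reading of FAS entry | Imputation | Tipping point | Rank sets |
|---|---|---|---|
| Any post-baseline score counts | both visits imputed under MAR | not shifted | in neither |
| A mapped Week 6 or 12 score is needed | outside the FAS | outside | outside |

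On the second reading the child also leaves the 3% and 5% counts, if these are taken in the FAS.

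**4. Triggers.** With 90 children, more than 3% means at least 3 (0.03 × 90 = 2.7) and more than 5% means at least 5 (0.05 × 90 = 4.5). Take 3 pattern-2 children and 2 with both missing. If all are counted, (3 + 2)/90 = 5.6%, above the 5% trigger. If the two leave the FAS, 3/88 = 3.4%, and neither the tipping point nor the rank test runs.

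**5. Size in the tipping point.** With about 45 per arm, m unshifted OV101 children reduce the arm-mean shift by m/45 per +1 step (ignoring the cap at 7). For m = 1 to 5 that is 0.022 to 0.111 per step, or 0.067 to 0.333 over three steps. If every missing OV101 value were of this kind, the step would change nothing and the loop would have no end.

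**6. Size in the rank test (extreme illustration, assumed data).** 45 per arm; all missing children lack both visits; scores 2/3/4 at the STARS rates in Protocol section 1, with all non-improvers set to 4. Placebo is 7.4/14.8/77.8%, OV101 combined 20.0/34.5/45.5%, OV101 QD 37.0/29.6/33.4%. The rates are applied to the remaining children and rounded. For a 5/0 loss at combined rates, the counts are 8/14/18 of 40 on OV101 against 3/7/35 of 45 on placebo. The test is a two-sided Wilcoxon, normal approximation, with tie and continuity corrections.

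| Missing, OV101/placebo | Combined rates: omitted | Combined rates: ranked lowest | QD rates: ranked lowest |
|---|---|---|---|
| 4/1 | 0.0035 | 0.047 | 0.0017 |
| 5/0 | 0.0020 | 0.084 | 0.0036 |
| 3/3 | 0.0040 | 0.012 | 0.0002 |

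**The case against.** The best defence concerns the FAS. Table 2 mapping is the default for all endpoints, and CGI-I-AS is scheduled only at Weeks 6 and 12. An assessment of the primary endpoint can therefore be read as a mapped score, and the two-pattern statement is then correct within the FAS. That reading is tenable, but it saves the count and not the analyses: the child disappears from both, and from the triggers, while the SAP says the rank analysis covers those who stopped before Week 12.

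Other points carry weight:

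- **The group is narrow.** The Day 6 rule stops drug, not participation, and Protocol 4.2 encourages continued visits; children who keep attending are unaffected. STARS discontinuations for adverse events were 1 on placebo, 0 on QD and 3 on BID.
- **There is partial cover.** Table 3 maps the early score to Week 6. The nominal-visit analysis, in which "records from the Day 43/Week 6 and Day 85/EOT/Week 12 visits will be included", might use it as Week 12. Disposition and missing-data tables would show an imbalance. None of these applies a penalty.
- **The illustration is extreme.** Only one of six cases crosses 0.05. The combined rates include a BID arm not used here, and the reported 34.5% minimally improved exceeds both arms' figures (29.6% and 32.1%), so it cannot be their pooled value.
- **The endless loop is not specific to this pattern.** It also arises if OV101 has no missing values or if the shifted values all reach 7. A stopping rule cures it.

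**Conclusion.** The concern holds. As written, both analyses exclude the earliest withdrawals, contrary to the SAP's stated aim for the rank test, and this is true on either reading of FAS entry.

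The size is unknown and may be nil. The goal of 80 completers from about 90 leaves room for about 10 non-completers (11%) for any reason, but the documents do not say how many would leave in the first week. The change in significance in the illustration depends on combined-dose STARS rates and all five losses falling on OV101; at QD rates the p-value stays below 0.005 in every case. The primary MMRM and the confirmatory testing sequence are untouched. It should be corrected before unblinding, because choosing the handling afterwards would be a post hoc decision in the analyses meant to test robustness to dropout.

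**What to change.** In SAP 3.8.6:

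1. Define a third pattern: Week 6 and Week 12 both missing.
2. Apply the same +1 steps to imputed OV101 Week 12 values in this pattern as in pattern 2.
3. Add a third, lowest-ranked set to the rank analysis for children with this pattern who discontinued, ordered by EOT CGI-I-AS where one exists. Visits missed without discontinuation, for example through pandemic restrictions, should not be penalised.

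In SAP 3.2.1:

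4. State whether FAS entry needs a score mapped to Week 6 or Week 12. If it does, run these two sensitivity analyses and compute the 3% and 5% triggers on all randomised and dosed 4 to 12 year olds.

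Items 1 to 3 cost a few sentences and some programming, with no new data; the sensitivity results may look slightly less favourable. The conditional part of item 4 costs more. SAP 3.8 and Protocol 7.8 base all efficacy analyses on the FAS and would need to be aligned, and Protocol 7.1 requires an amendment if the change is judged substantial. Items 1 to 3 do not depend on that step, but if FAS entry needs a mapped score they reach these children only once it is taken.

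### The multiple-imputation step for missing Week 6 CGI-I-AS omits the observed Week 12 score, so the model used to impute dropouts is attenuated; the effect is small and its sign depends on which arm loses more children

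*SAP*

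**What the plan says.** SAP 3.8.6 brings in multiple imputation conditionally: "If more than 3% of CGI-I-AS values at Week 12 are missing, as a sensitivity analysis". It names two patterns: Week 6 missing with Week 12 present, and Week 12 missing with Week 6 present. For the first it accepts MAR "because the data before and after the intermittent missing value are known", and it applies that reasoning to this trial: "if Week 6 CGI-I-AS is missing but Week 12 CGI-I-AS is assessed (missing data pattern 1), it is reasonable to consider" the gap MAR.

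The procedure then runs in order.

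- Step 1: "Missing Week 6 CGI-I-AS data points will be imputed under MAR assumption using a logistic regression model for ordinal data with randomized treatment". The full predictor list is "randomized treatment, age group, region, and CGI-S-AS Overall Score at Baseline as independent variables".
- Step 2 imputes missing Week 12 scores from the same terms with the Week 6 score added: "CGI-S-AS Overall Score at Baseline, and the Week 6 CGI-I-AS as independent variables".
- "Thirty complete imputed datasets will be generated by repeating the above steps 30 times". The primary MMRM is fitted to each data set and the results are combined.

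The tipping-point analysis in the same section starts from these 30 data sets. It is run only if the MAR result is significant and more than 5% of Week 12 values are missing. SAP 3.8.6 later repeats the two steps, with linear regression, for a set of redacted secondary endpoints. Nowhere does the SAP add Week 12 to step 1 or limit the step 2 fit to children with both scores observed.

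**The concern.** The SAP's reason for MAR and its imputation model do not match. MAR for a Week 6 gap is credible here because the Week 12 score is observed, and imputation under MAR has to condition on what is observed. Step 1 leaves out the most informative observed value.

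The damage is indirect. A child with Week 12 but not Week 6 needs no imputation for the Week 12 comparison. But if that child enters the step 2 fit with a Week 6 value drawn without regard to the child's own Week 12 score, the fitted link between visits weakens. Step 2 is the model that imputes Week 12 for dropouts. With a weaker link, a dropout with a poor Week 6 score is pulled towards the average. At stake are the MAR sensitivity estimate, its significance (which decides whether the tipping-point analysis is run) and the starting values of that analysis.

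**Working it through.** The documents give no figure for this step, and the Protocol 7.3 sample-size text is not available, so there is no stated number to reproduce.

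**Inputs from the documents.** About 90 children randomized 1:1 (SAP 2.2.1). At least 80 evaluable completers sought (Protocol 4.2.3), so the allowed loss is (90 − 80)/90 = 11.1%. The imputation trigger is 3% of 90 = 2.7, that is, 3 or more children. Thirty imputations.

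**Assumed inputs, not in the documents.** Correlation between Week 6 and Week 12 of 0.4 to 0.8; latent SD 0.9; true effect −0.6 points (lower is better, so a negative shift favours OV101); worse Week 6 scores more likely to drop out.

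**1. Attenuation.** Let f be the fraction of children with an observed Week 12 score who lack Week 6. Suppose their Week 6 values are replaced by draws with the right spread but no relation to Week 12 given treatment. The within-arm covariance becomes (1 − f) × cov(W6, W12) and the Week 6 variance is unchanged, so

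slope after step 1 = (1 − f) × true slope.

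A large-sample check (n = 40,000, 7-point scores, correlations 0.4, 0.6 and 0.8) agrees:

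| f | Linear slope / true | Ordinal-logit coefficient / true |
|---|---|---|
| 2% | 0.98 | 0.97–0.98 |
| 5% | 0.95 | 0.91–0.95 |
| 10% | 0.90 | 0.83–0.90 |
| 20% | 0.80 | 0.70–0.78 |

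The ordinal coefficient, the kind the SAP uses, falls somewhat more than f at high correlation. With Week 12 added to step 1, both ratios return to 0.99–1.01.

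**2. Effect on the treatment estimate.** Simulated trials of 90 children, 250 per scenario, 30 imputations, Rubin's rules, normal-linear imputation standing in for ordinal logistic, and the Week 12 mean difference as the estimate. Shift = SAP method minus corrected method.

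| Correlation | f | Week 12 missing | Who drops out | Shift |
|---|---|---|---|---|
| 0.6 | 0 | 11% | OV101 only | 0.000 |
| 0.6 | 2% | 5% | OV101 only | −0.002 |
| 0.6 | 5% | 5% | OV101 only | −0.003 |
| 0.6 | 5% | 11% | OV101 only | −0.009 |
| 0.6 | 10% | 11% | OV101 only | −0.016 |
| 0.8 | 10% | 11% | OV101 only | −0.022 |
| 0.8 | 20% | 11% | OV101 only | −0.042 |
| 0.6 | 10% | 11% | equal numbers per arm | +0.001 |

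The SD of the trial estimate was about 0.21 to 0.22. A separate simulation at correlation 0.6 and 11% missing gave −0.008 (f = 5%) and −0.016 (f = 10%) with OV101-only dropout. With one common Week-6-driven rule in both arms it gave about 0.000 and +0.003. Another run with a common rule and 10% dropout gave +0.004 to +0.007 at f = 10%.

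**3. Why the sign turns.** The shift in an arm's mean is roughly −(share of the arm imputed) × (loss of slope) × (Week 6 gap between dropouts and the rest). In the −0.016 case the share is 10/45 = 0.222 and the slope falls from 0.547 to 0.485, a loss of 0.062; the implied gap is 0.016/(0.222 × 0.062) ≈ 1.2 points. The same pull acts on placebo dropouts. With equal numbers it cancels. With a common rule, placebo has the worse Week 6 scores and loses more children, so the pull helps placebo more.

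**4. Scale.** 0.016/0.21 ≈ 0.08 of the SD of the estimate. One tipping-point step adds 1 point to each imputed OV101 value, moving that arm's mean by up to 10/45 = 0.22 points if all 10 losses are on OV101; 0.016 is about 7% of that step. In the −0.016 scenario the imputed result was significant in 202 of 250 trials (0.808) by the SAP method and 194 of 250 (0.776) by the corrected one.

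**The case against.** The strongest reply is that this cannot move the trial's conclusion. The primary MMRM does not impute, multiple imputation is a conditional sensitivity analysis, tipping-point steps are whole scale points, and above 5% missing the SAP adds a rank-based analysis that needs no imputation. All of that stands and fixes the low priority.

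Second, the SAP does not say which children enter the step 2 fit, and it defers to a published imputation strategy not available here. If step 2 were fitted only to children with both scores observed, there would be no attenuation. The sequential wording points the other way, but the SAP should say so.

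Third, a reader might infer that the rule favours OV101. The documents do not support that. It needs Week-6-related dropout concentrated on OV101, and they give no dropout rates by arm. Under a common rule the shift is nil or slightly the other way.

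Fourth, a reader might infer that pandemic disruption will make Week 6 gaps frequent and the bias large; at 30% Week 6 missing with OV101-only dropout the shift did reach −0.051. The documents do not support that scenario either. The Pandemic Addendum (Protocol 13) allows remote CGI-I-AS rating at Week 6, so a remote visit yields a score, and SAP Table 2 maps unscheduled and early end-of-treatment assessments from Day 22 to Day 64 to Week 6, a span of 43 days.

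**Conclusion.** The point holds as a flaw in the specification with a small numerical effect. The SAP justifies MAR by the known later score and then does not use it. On the plain reading, the step 2 coefficient for Week 6 is attenuated by roughly the fraction of Week-12-observed children who lack Week 6.

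The treatment estimate shifts by about 0.01 to 0.02 points in OV101's favour at 5–10% Week 6 missing with OV101-only dropout, and by nothing to a few thousandths against OV101 when one rule governs both arms, against an SD of about 0.2. Harm requires both missing patterns together.

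These sizes rest on an assumed correlation of 0.6, 11% Week 12 missing, the assumed dropout mechanism, and a normal-model stand-in for the ordinal imputation. The attenuation itself needs only that step 2 is fitted with the imputed Week 6 values.

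**What to change.** Either of two changes to SAP 3.8.6 removes the problem.

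- Add the observed Week 12 CGI-I-AS as a predictor in step 1, for example with fully conditional specification in PROC MI and ordinal logistic models for both visits, which suits the non-monotone pattern.
- Or leave intermittent Week 6 values unimputed, fit step 2 only on children with both scores observed, and let the MMRM handle the gaps. By the SAP's own definition, children in the second pattern have Week 6 observed, so step 1 is not needed to impute their Week 12 score.

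Make the same change to the parallel scheme for the redacted secondary endpoints, and state which children enter each fit.

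The cost is a line or two of SAP text and minor reprogramming. The first option should name a fallback, because an ordinal model on a 7-level score in about 90 children may fail to converge when categories are sparse; the present plan has the same exposure.
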